3.3.8 Change from baseline in Quality of Life (QOL) questionnaires (EQ-5D, SF-36)

QOL Questionnaires (EQ-5D and SF-36) will be completed by patients at Baseline, Week 13, Week 26 and Week 52 and Week 65.

A shift table for EQ-5D QOL Questionnaire will be provided with the shift from the **Index Study Baseline** level and from the **Open-label Study Baseline** level for each dimension (mobility, self-care, usual activities, pain/discomfort, and anxiety/depression) to post-baseline visit level. In the shift table, slight and moderate will be combined as one level, and severe and unable will be combined as one level. The health status visual acuity score (VAS), as well as the scores for all dimensions, will be summarized for baseline, post-baseline visit, and the change from baseline at post-baseline visit will be summarized also.

The results of the mean weighted scores for all sections from the SF-36 QOL Questionnaire (vitality, physical functioning, bodily pain, general health perceptions, physical role functioning, emotional role functioning, social role functioning, and mental health) will be summarized for baseline, post-baseline visit, and the change from baseline at post-baseline visit will be summarized also. Both the **Index Study Baseline** and the **Open-label Study Baseline** will be used.

Note: Group 2 patients have no QOL assessment in the index study (ISIS 304801-CS16).

3.3.9 Adjudicated acute pancreatitis events Rate

Yearly rate of adjudicated acute pancreatitis events and patient reported moderate or severe abdominal pain (pain score: 4-10) for FAS during the on-treatment period of the Open-label study, calculated as $365.25 \times \text{the number of events during the on-treatment period} / \text{on-treatment duration}$, will be summarized with descriptive statistics. At each mapped visit window of abdominal pain, at most one moderate or severe event will be counted to calculate the yearly rate. Adjudicated acute pancreatitis event rate prior to first dose of Study Drug (including events based on medical chart review) vs. treatment emergent events will be summarized.

Yearly rate of adjudicated acute pancreatitis events and patient reported moderate or severe abdominal pain (pain score: 4-10) for patients who administered volanesorsen in Index studies will be calculated and summarized, including events occurred during either index study or open-label study.

On-study and on-treatment pancreatitis incidence rate per patient year of exposure will be summarized.

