3 ANALYSIS PLAN

3.1 Statistical Design Summary

This is a multi-center open-label study of:

Group 1: ISIS 304801-CS6 (index study) roll over FCS patients

Group 2: ISIS 304801-CS16 (index study) roll over FCS patients

Group 3: FCS patients who did not participate in the ISIS 304801-CS6 or ISIS 304801-CS16 index studies.

Group 1 and Group 2 patients who complete one of the index studies and who are qualified plus Group 3 patients who are screened and qualified will be enrolled to this open-label study. The safety and efficacy of extended dosing with volanesorsen in patients with FCS will be evaluated by summary tables rather than hypothesis tests. Missing data will not be imputed.

3.1.2 *Sample Size Consideration*

No sample size calculations were performed as this is an open-label extension study.

3.1.3 *Planned Interim Analysis*

An interim analysis may be conducted after the last patient's Week 13 visit of the open-label study or after the database of the ISIS 304801-CS6 and ISIS 304801-CS16 index studies are locked and unblinded.

Planned summaries and patient data listings for disposition, demographic, efficacy and safety will be included in this interim analysis.

Additional interim analyses will be performed to support regulatory filing activities.

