3.3 Efficacy Analysis

Efficacy endpoints include: percent change and change in fasting lipid measurements, frequency and severity of patient reported abdominal pain, change from baseline in QOL, adjudicated acute pancreatitis events rate and frequency of other symptoms.

Efficacy analyses will be conducted in the FAS by the group presented in [Section 3.2.1](#).

For fasting lipid measurements and QOL (EQ-5D, SF-36), both the **Index Study Baseline** and the **Open-label Study Baseline** will be used. In the summary tables using the **Open-label Study Baseline**, visits are mapped to analysis visits as shown in [Section 3.2.1](#) for fasting lipid measurements and QOL (EQ-5D, SF-36) in the open-label study. In the summary tables using the **Index Study Baseline**, visits include the index study baseline visit, and the open-label study mapped post baseline visits.

Efficacy analyses for the fasting TG will be performed on FAS.

By patient listings will have all efficacy endpoints results collected in the open-label study.

Summary table and by patient listing will be generated by visit window, dose level, fasting TG and corresponding change from baseline value, nadir platelet, any pre-treatment adjudicated pancreatitis events, and abdominal pain event (average of intensity and yearly rate of frequency of moderate or severe events). Below visit windows will be utilized:

Visit Window	Dose Level	TG	Platelet Nadir	Abdominal Pain
0-3 months	week 1-13	month 3	day 1-91	week 2-14
3-6 months	week 14-26	month 6	day 92-182	week 15-27
6-9 months	week 27-39	week 38	day 183-273	week 28-40
9-12 months	week 40-52	month 12	day 274-364	week 41-53
12-15 months	week 53-65	week 64	day 365-455	week 54-66
15-18 months	week 66-78	week 76	day 456-546	week 67-79
18-21 months	week 79-91	week 90	day 547-637	week 80-92
21-24 months	week 92-104	week 104	day 638-728	week 93-105
24-27 months	week 105-117	week 117	day 729-819	week 106-118

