3.3.5 Frequency and severity of patient reported abdominal pain

The maximum intensity of abdominal pain related to disease will be collected on the FCS symptom questionnaire and reported by patients weekly on Bracket electronic patient reported outcomes (ePRO). The average maximum intensity of patient reported abdominal pain score during the on-treatment period will be summarized. The patients' reported results will be mapped to each visit week based on the visit window specified in [section 3.2.1](#). If patients have multiple results within a visit window, the worst score will be used for summary and analysis. The results at Week 1 will not be included in the on-treatment period, since the results are reported retrospectively to collect the symptoms of patients during the past week. The missing data will be imputed by using Next Observation Carried Back (NOCB) if there is a subsequent score available. Otherwise, the missing data after the last available score of each patient will not be imputed.

Two (2) types of summary tables will be provided in the subset of FAS patients who reported any abdominal pain (pain score > 0) during the screening period and Week 1. Baselines are defined in the [section 3.2.3](#).

1. Change from both **Index Study Baseline** and **Open-label Study Baseline** in the average of maximum intensity of patient reported abdominal pain will be summarized.
2. Change from both **Index Study Baseline** and **Open-label Study Baseline** in the worst weekly patient reported maximum intensity abdominal pain score during the treatment period will be summarized.
3. The same method described above will be used to impute the missing data in exploratory analyses.

The abdominal pain score in each week will be categorized to no pain (pain score: 0), mild (pain score: 1–3), moderate (pain score: 4–6), or severe (pain score: 7–10). A summary by the category will also be provided for safety set overall, and for CS6 subjects who roll-over to CS7. Other information of the abdominal pain questionnaires will be listed in a patient data listing.

Summary table and figure for abdominal pain intensity change for patients with pain at baseline in CS6 subjects who roll-over to CS7 will be generated.

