3.5 Safety Analyses

Safety endpoints including treatment exposure, AEs, clinical safety lab, vital signs, physical examination, 12-lead ECG, Echocardiogram, prior and concomitant medication use, and MRIs will be summarized in Safety Set.

On-Study period (from **Day 1 of Volanesorsen** to end of the study) in the open-label study will be classified to 3 periods:

- On-treatment period: from the first dose of Volanesorsen to the last dose of Volanesorsen + 28 days
- After-treatment period: from the last dose of Study Drug + 29 days to the last dose of study medication + 90 days
- Post-follow up period: after the last dose of Study Drug + 90 days

For vital sign, clinical safety lab, or 12-lead ECG,

- Visits of summary tables include baseline and labeled post baseline visits in the open-label study.
- **Safety Baseline** is defined in the [section 3.2.3](#) of this SAP.

For AEs, prior and concomitant medication use, each summary table will present the open-label study data.

For treatment exposure, details are discussed in the [section 3.5.5](#) of this SAP.

By patient data listings will display data collected in the open-label study.

In this section, **Day 1 of Volanesorsen** is defined as the first day volanesorsen is administered to the patient. For patients on active treatment in the index study, Day 1 of Volanesorsen will be the first day volanesorsen is administered in the index study. For patients on placebo in the index study, Day 1 of Volanesorsen will be the first day volanesorsen is administered in this open-label study.

Patient profile figures will be generated for selected patients to provide graphical profile of endpoint of interest.

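### The yearly abdominal pain rate divides diary events by dosing time, so on-treatment weeks after a patient's last diary entry count as pain-free, and the SAP does not say whether back-filled weeks count as events

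*SAP*

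**What the plan says.** Section 3.3.9 defines the yearly rate as 365.25 times the number of on-treatment events divided by on-treatment duration. It applies this both to adjudicated acute pancreatitis and to patient-reported pain scored 4 to 10. For pain it adds: "At each mapped visit window of abdominal pain, at most one moderate or severe event will be counted to calculate the yearly rate". A second paragraph plans the same rates over index and open-label time combined, for patients given volanesorsen in the index studies.

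Section 3.5 sets the period by dosing: "On-treatment period: from the first dose of Volanesorsen to the last dose of Volanesorsen + 28 days".

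Section 3.3.5 describes the pain data. Scores are reported weekly on an electronic diary and mapped to weekly windows. Three rules matter here:

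- Week 1: "The results at Week 1 will not be included in the on-treatment period".
- Gaps before a later score: "The missing data will be imputed by using Next Observation Carried Back (NOCB) if there is a subsequent score available".
- Weeks after the last score: "Otherwise, the missing data after the last available score of each patient will not be imputed".

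Section 3.3 also tabulates a yearly rate of moderate or severe pain by 3-month window, out to 24-27 months, and states no denominator. Section 3.1 says, without exception, "Missing data will not be imputed".

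**The concern.** The two outcomes sharing the formula are observed differently. Pancreatitis reaches the analysis through adverse event reporting and adjudication, so time on treatment is a fair denominator. Pain is seen only in weeks when the patient completes the diary. A dosed week with no score adds seven days to the denominator and cannot add an event, so it is treated as pain-free.

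After the last score this follows directly from the rules, because those weeks are never filled. For earlier gaps, section 3.3.9 neither adopts nor excludes NOCB, and the two readings give different counts.

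The rate therefore falls when patients give up the diary while still dosed, with no change in pain. In a long extension that can look like improvement over time. The 3-month table would show it most clearly if the 3.3.9 formula is carried over, because a window with no diary would then read 0 per year instead of missing.

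The pooled index plus open-label rate has the same weakness. The SAP does not say whether CS16 collected the pain diary, and section 3.2.3 defines an index-study pain baseline for Group 1 only. If CS16 did not collect it, CS16 patients' index period would add only event-free time.

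**Working it through.** The SAP gives no expected rate or diary completion figure, so there is no stated result to reproduce. The check applies its formula to an assumed patient.

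**Inputs from the SAP.** Week 52 is Day 358 (section 1.4). The on-treatment period ends 28 days after last dose (3.5). Pain windows are 7 days wide, with target day (n-1) x 7 + 1 (3.2.1). Week 1 is excluded (3.3.5).

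**Assumptions.** Last dose on Day 358; a constant true rate of 12 event-weeks per year; diary complete up to a stopping week and absent afterwards.

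**Denominator.** 358 + 28 = 386 days. The last window with its target day on treatment is Week 56 (55 x 7 + 1 = 386), so Weeks 2-56 give 55 windows.

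**Rate under 3.3.9.** With S scored weeks, expected events are S x 12 x 7 / 365.25, so the rate is 12 x 7 x S / 386.

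| Diary ends after | S | SAP rate per year | Shortfall against 12 |
|---|---|---|---|
| Week 56 | 55 | 11.97 | 0.3% |
| Week 52 | 51 | 11.10 | 7.5% |
| Week 39 | 38 | 8.27 | 31% |
| Week 26 | 25 | 5.44 | 55% |
| Week 13 | 12 | 2.61 | 78% |

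The SAP rate as a fraction of the true rate is 7S / 386. For example, at Week 26 it is 175 / 386 = 0.453. It does not depend on the assumed event rate.

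**One score after a gap.** Suppose a patient misses k weeks and then reports a score of 4 or more. Without NOCB that is 1 event; with NOCB it is k + 1. For k = 10:

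- Without NOCB: 365.25 x 1 / 386 = 0.95 per year.
- With NOCB: 365.25 x 11 / 386 = 10.41 per year.

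If the score after the gap is below 4, the filled weeks add no event.

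**Random gaps.** A simulation used 40,000 patients, 55 weeks, a weekly event probability of 12 x 7 / 365.25 = 0.230, and independent gaps. The scored-week rate is 365.25 x event-weeks / (7 x scored weeks).

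| Completion | SAP formula, no NOCB | SAP formula, NOCB (SD) | Scored-week rate (SD) |
|---|---|---|---|
| 90% | 10.76 | 11.93 (3.24) | 11.99 (3.11) |
| 75% | 8.97 | 11.88 (3.80) | 11.99 (3.44) |
| 50% | 5.98 | 11.73 (5.01) | 11.99 (4.22) |

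The means agree with direct calculation. Without NOCB at 50% completion, 11.97 x 0.5 = 5.98. With NOCB at 50%, about one trailing week stays unfilled on average, so 11.97 x 54 / 55 = 11.75.

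**3-month table.** Weeks 2-14 are 13 windows, or 91 days. If the 3.3.9 formula were used with 91 days per window, a patient at 12 per year whose diary stops after Week 27 would show 12.0 (13 x 0.230 = 2.99 events; 365.25 x 2.99 / 91), then 12.0, then 0 and 0 for the 6-9 and 9-12 month windows, with no change in pain.

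**The case against.** The strongest reply is that section 3.3.5 governs all pain data, including frequency, and extends its imputation to exploratory analyses. A programmer could reasonably use NOCB-filled scores in 3.3.9. On that reading random gaps cause almost no average bias, as the second table shows, and only a cross-reference is missing. The extra spread under NOCB also rests on pain being independent from week to week; correlated pain would reduce it. This has force for intermittent gaps. It does not help after the last score, where nothing is filled on any reading.

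The large shortfalls need a patient who abandons the diary but keeps dosing, and the SAP gives no evidence on how common that is. Patients who stop treatment contribute little, because their denominator stops 28 days after last dose. That limits the likely size but not the direction.

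The 3-month table states no denominator, so a false zero there is conditional. Average intensity appears in the same table and would be missing in an empty window, which would alert a careful reader. Other pain summaries, by category and by average or worst intensity, do not divide by on-treatment duration.

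Finally, a scored-week rate is unstable when few weeks are scored: one scored week of 4 or more gives 365.25 / 7 = 52.2 per year. In a study of up to about 70 patients, a few sparse diaries could move the mean and maximum. That is a real cost, and reporting scored weeks makes it visible.

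**Conclusion.** The concern holds. Followed exactly, the SAP counts dosed weeks without a diary after the last score as pain-free, which biases the pain rate downward. On-treatment duration is not defined as a separate term, but the period in 3.5 and the treatment duration in 3.5.5 are both set by dosing, so neither reading makes it diary-based. Whether gaps before a later score also count as pain-free depends on an NOCB rule that 3.3.9 does not state.

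The direction is certain wherever the diary ends before the on-treatment period does. The size depends on adherence, which is not given: in the worked patient the shortfall runs from 7.5% (diary to Week 52) to 78% (diary to Week 13), and it is negligible when the diary is complete. The pancreatitis rate is unaffected.

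The study has no primary efficacy endpoint and no formal hypothesis, so no error rate is at stake. Descriptive tables are its efficacy output, however, and the frequency of abdominal pain is a listed endpoint, so this should be corrected. The conflict between 3.1 and 3.3.5 on imputation is separate and minor.

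**What to change.** In section 3.3.9, for abdominal pain only, define:

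yearly rate = 365.25 x (on-treatment weeks from Week 2 with an observed score of 4 or more) / (7 x on-treatment weeks from Week 2 with an observed score).

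- Use it in the open-label summary, the pooled index plus open-label summary and the 3-month table in 3.3. Set it to missing when no week is scored.
- State that NOCB-filled weeks enter neither the numerator nor the denominator of this rate.
- Keep on-treatment duration for adjudicated pancreatitis.
- Report the number of scored weeks beside each rate.
- In 3.1, name the NOCB rule of 3.3.5 as an exception.
- Say in the report that the rate remains biased if diaries are missed because of pain.

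The cost is SAP wording and one changed denominator in the pain-rate program. No new data are needed. Per-patient rates become less stable where few weeks are scored.

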3.3.10 Frequency of other symptoms: eruptive xanthoma, lipemia retinalis

Percentage of patients who experienced eruptive xanthoma during the treatment period of the Open-label study will be summarized. Counts and percentages of the worst severity of eruptive xanthoma will be provided. Yearly rate during the treatment period of the Open-label study, calculated as $365.25 \times$ the number of events during the treatment period / treatment duration, will be summarized with descriptive statistics.

Yearly rate of eruptive xanthoma for patients who administered volanesorsen in the Index study CS6 will be calculated and summarized, including events occurred during either index study or open-label study.

Counts and percentages of lipemia retinalis will be summarized by visits.

3.4 Pharmacokinetic and Immunogenicity Analysis

PK concentration and Immunogenicity (IM) results obtained in the open-label study will be summarized along with those from the index study. Patient data listings will also be provided.

3.4.1 Pharmacokinetic Analysis

PK analyses will be conducted in PK population.

3.4.1.1 All patients

During the treatment period, blood samples for the determination of plasma volanesorsen concentrations will be collected prior to dosing, and at various times throughout the dosing and post-treatment follow-up period as noted in the tables below.

PK Sampling Schedule (All Patients except PK Subgroup)

Week	Wk 1	Wk 4	Wk 8	Wk 13	Wk 26	Wk 38	Wk 52	Wk 65*
Study Day	D1	D22	D50	D85	D176	D260	D358	D449
Visit Window +/- Days	0	2	2	2	2	3	2	7
Time Point	Pre-dose	Anytime						

* Week 65 PK collection will be omitted for patients continuing to receive volanesorsen beyond Week 52

PK Sampling Schedule (Extended Treatment Period)

Week	Wk 76	Wk 104	Wk 117
Study Day	D526	D722	D813
Visit Window	2	2	7

+/- Days			
Time Point	Pre-dose	Pre-dose	Anytime

For all patients, plasma concentrations of volanesorsen, along with the scheduled (nominal) and actual sampling times (i.e., time from SC dosing) will be listed (when applicable) for Group 1 and Group 2 patients by their prior treatment in Study ISIS 304801-CS6 and ISIS 304801-CS16 and newly enrolled patients as a separate group (Group 3), dose, patient ID, patient immunogenicity (IM) status, and IM onset (if applicable) as defined in [Section 3.4.2](#), and day. Plasma concentrations below the lower limit of quantification (LLOQ) will be presented as "0.00". In addition, percent differences between scheduled and actual sampling times will also be listed.

For all patients, trough (pre-dose) and post-treatment volanesorsen plasma concentrations will be summarized by the group presented in [Section 3.2.1](#), study day, with and without stratification by IM status, using descriptive statistics (n, mean, SD, SEM, %CV, geometric mean, geometric %CV, median, minimum, and maximum). For the purpose of calculating typical descriptive statistics for plasma concentrations, all below the lower limit of quantification (BLQ) values will be set to zero. Mean plasma concentrations that are BLQ will be presented as BLQ, and the SD and %CV will be reported as "NA" (not applicable). At the discretion of the pharmacokineticist and/or biostatistician, samples may be excluded from descriptive statistics if there are large deviations between scheduled and actual sampling times, or large deviations between actual dose and nominal dose.

Mean (\pm SD) plasma volanesorsen concentration-time plots with and without stratification by immunogenicity status will be generated.

3.4.1.2 PK subgroup

A subgroup of patients will participate in an extended PK collection. The detailed PK sampling schedules are outlined below. Patients continuing to receive volanesorsen beyond Week 52 will follow the PK sampling schedule in the extended treatment period:

PK Sampling Schedule (PK Subgroup only*)

Week	Wk 1	Wk 1	Wk 4	Wk 8	Wk 13	Wk 26	Wk 38	Wk 52	Wk 65**
Study Day	D1	D2	D22	D50	D85	D176	D260	D358	D449
Visit Window +/- Days	0	0	2	2	2	2	3	2	7
Time Point	Pre-dose, 1, 2, 3, 4, 6, 8, and 12 hrs post-dose	24 hrs post-dose	Pre- dose	Pre- dose	Pre- dose	Pre- dose	Pre- dose	Pre- dose	Anytime

* Patients at selected sites will be asked to participate in the extended 24-hour PK profile beginning on Study Day 1. Participation is optional

** Week 65 PK collection will be omitted for patients continuing to receive volanesorsen beyond Week 52

For patients in the PK subgroup only, non-compartmental PK analysis of volanesorsen will be carried out on each individual patient data set using data collected in the open-label study from the intensive PK subgroup, following a single dose (i.e., single-dose PK) or multiple doses (i.e., steady-state PK), depending on their earlier treatment in the index studies (Group 1 and Group 2 Patient). On Week 1 Day 1 of the open-label study, patients who received placebo in the index study (and all patients in Group3) will receive the first treatment of volanesorsen (single-dose PK), while patients who received volanesorsen in the index studies had been on volanesorsen treatment for 12 months (ISIS 304801-CS6) or 6 months (ISIS 304801-CS16), thus the PK data collected from these patients reflect steady-state PK. The maximum observed drug concentration (C_{\max}) and the time taken to reach C_{\max} (T_{\max}) will be obtained directly from the concentration-time data. Area under the plasma concentration-time curve from time zero to 24 hours (AUC_{0-24h}) will be calculated using the linear trapezoidal rule. Apparent systemic (plasma) clearance after SC administration (CL_{0-24h}/F) will be calculated from $CL_{0-24h}/F = \text{Actual Dose}/AUC_{0-24h}$. Mean residence time (MRT) from time zero to 24 hours after the SC administration will be calculated from the equation, $MRT_{0-24h} = AUMC_{0-24h}/AUC_{0-24h}$, where $AUMC_{0-24h}$ is the area under the moment plasma concentration-time curve from time zero to 24 hours after the SC administration. Other PK parameters, as appropriate, may be determined or calculated at the discretion of the PK scientist.

Plasma PK parameters will be summarized using descriptive statistics for 2 groups (Treatment naive group and CS6-Volanesorsen and CS16-Volanesorsen Combined), with and without stratification by IM status.

Population PK, PK/PD, and covariate analysis may be performed if deemed appropriate, and results will be reported separately. This SAP do not include relevant analysis plan.

